7.3 Selection of population for investigation

7.3.1 Inclusion Criteria

Subjects must meet all criteria listed below to be included in the investigation:

- **1.** Acute wound: traumatic wound (dermabrasion, skin tears, other), small burns 1st and 2nd degree requiring the use of dressings
- **2.** Acute surgical wound
- **3.** Acute wound size between 3 cm² and 24 cm² (wound could be covered by 2 investigational products maximum)
- **4.** Wound whose duration is ≤ 3 days
- **5.** Both gender with an age ≥ 18 years
- **6.** Written confirmation from the study nurse that the patient was informed, orally agreed to participate and to comply with study treatment and planned visits
- **7.** Subject able to follow the protocol

7.3.2 Exclusion Criteria

A subject will be excluded from the investigation if he/she meets any of the following criteria:

- 1. Infected, moderately to strongly exudative and haemorrhagic wound
- **2.** Diagnosed underlying disease (e.g. diabetic neuropathy, stroke, etc) which as judged by the investigator could interfere with the pain assessment
- **3.** Known allergy/hypersensitivity to any of the components of the investigational products
- **4.** Participation in other clinical investigation within one month prior to start of investigation
- 5. Pregnant or breast-feeding women
- **6.** Person protected by a legal regime (tutorship or guardianship)
- **7.** Patients unable to manifest an oral consent to participate (e.g. dementia) or to understand the use of the VAS tool.
- 8. Patient not covered by health insurance/social security

Definitions:

Acute wound: wound without any local or general factor that could delay healing (unlike chronic wound). For this investigation, only acute wound with a skin barrier break with loss of dermis will be included.

Dermabrasion: skin lesions of traumatic origin (superficial abrasion) caused by tangential friction forces at the surface of the epidermis and the dermis.

Skin tears: traumatic injuries which can result in partial or full separation of the outer layers of the skin. These tears may occur due to shearing and friction forces or a blunt trauma, causing the epidermis to separate from the dermis (partial thickness wound) or both the epidermis and the dermis to separate from the underlying structures (full-thickness wound).

Burn: small burns of the 1st degree and light 2nd degree; dynamic injuries induced by traumatic destruction of the skin < 10%.

First degree burn and second degree superficial burn without any severity factor (as age > 60 years, vital/functional location, associated lesion, previous injuries/illnesses) are considered as benign burn.

For this investigation, only burn induced by a thermal process will be included.

7.3.3 Early Termination/ Withdrawal of subjects from treatment or assessment

Patients are free to withdraw from participation in the study at any time upon request and without any disadvantages for their further care.

An investigator may discontinue a patient from the study for the following reasons:

- The identification of unacceptable risks, or incidents leading to an unacceptable benefit-risk assessment
- Premature termination of the investigation decided by the Sponsor
- Lost to follow-up
- Occurrence or development of a condition described in the exclusion criteria (i.e. pregnancy, infection of the wound) throughout the investigation
- Death

The reason for patient discontinuation or withdrawal from the study will be recorded on the Case Report Form (CRF) in the early termination visit.

Subjects who discontinue the investigation should always be asked about the presence of any Adverse Events/Adverse Device Effects or Device Deficiencies and, if possible, be assessed by the investigator as per the list of the Early termination visit procedures. Serious Adverse Events/Adverse Device Effects should be followed up until the resolution of the event.

7.4 Investigational device

7.4.1 Description of Lomatuell Pro®

Lomatuell Pro® is a wound contact layer consisting of wide-meshed tulle, impregnated with a polymer matrix, which form a gel on contact with wound exudate to facilitate moist wound healing.

It offers a solution to the challenge of dressings/residue sticking to the wound or wound, which may cause pain and trauma on removal.

Key benefits

- Gel formation supports moist wound healing
- Dressing changes are atraumatic and virtually painless
- Effective transfer of exudate into the secondary dressing
- Less disturbance of the wound bed: intervals between dressing changes may be extended
- Conforms well to the contours of the wound bed, meaning all the areas benefit from the moist properties
- Either side can be applied, eliminating concerns over incorrect application

Indications:

Wounds with no or low levels of exudate, or combined with an appropriate absorbant dressing for moderate to highly exuding wounds including:

- Chronic wounds e.g. leg ulcers, diabetic ulcers and pressure ulcers
- Acute wounds e.g. lacerations, cuts, abrasions and superficial epidermal and partial thickness burns
- Surgical wounds e.g. surgical wounds healing by secondary intention, toenail avulsions and skin graft and donor sites

Precautions:

Do not use if there is a known sensitivity to the product or any of its components

Wear time:

Average 2 to 4 days, and up to 7 days. Intervals between dressing changes must be determined by the clinician based on the condition of the wound, level of exudate and secondary dressing.

7.4.2 UrgoTul®

UrgoTul® is a flexible contact layer with TLC healing matrix comprised of a conformable polyester mesh impregnated with hydrocolloid and petroleum jelly particles.

Indications:

UrgoTul® is indicated for the treatment of non to low exuding wounds in the epithelialisation stage (burns, abrasions, traumatic wounds, post-operative wounds, leg ulcers, pressure ulcers, diabetic foot ulcers, epidermolysis bullosa).

Mode of action:

When in contact with wound exudate, UrgoTul® gels and creates a moist environment, promoting healing. UrgoTul® stimulates fibroblast proliferation and ensures non-adherence and pain-free dressing changes.

Wear time:

UrgoTul® should be changed every 2 to 4 days (up to 7 days) depending on the level of exudate and the clinical condition of the wound.

7.5 Secondary dressings and fixation

A secondary dressing could be applied on the investigational product. In case of exuding wound, secondary dressing should be applied. Investigational products could be used as protective layer only if the wound is not exuding.

List of possible secondary dressings and fixation (as an example):

Secondary dressings

Hydrocolloid dressings

- Foam dressings
- Dry dressings with or without adhesive border (like Vliwasorb or Vliwazell, gauze)

Wound filler (if necessary)

- Alginate dressings
- Hydrofiber (CMC) dressings

Fixation

- Compresses
- Form dressings

7.6 Concomitant Treatment

All medication which is considered necessary for the subject's safety and well-being may be given at the discretion of the investigator.

All concomitant medication and relevant treatment must be recorded in the appropriate section of the Case Report Form (CRF).

For analgesic treatment all data including type of analgesic, frequency of use before wound treatment (at D0 only) and hour of intake before dressing removal must be recorded in the appropriate form of the CRF.

7.7 Evaluation by W.H.A.T

The evaluation by the W.H.A.T. system will be performed by Lohmann & Rauscher with the photographs sent by RCTs on USB Keys.

For determination of the size of the wound area and recording of occurrence of necrotic/fibrinous/ granulation/ epithelisation tissue the validated Wound Healing Analysing Tool (W.H.A.T.) will be used. The wound dressing should be removed from the lesion. The wound should be cleaned with isotonic saline solution and the rest of remedies should be removed. After cleaning the ruler must be placed close to the wound. To achieve a correct picture, the ruler with the square mark had to be placed in the same plane as the lesion. In the case the wound was not plane the ruler has to be applied in the same shape to allow an authenticable digital reproduction of the wound. One digital picture of the lesion will be taken at each visit (in total three pictures of the lesion for each patient for the whole duration of the study); a minimal resolution of 3.0 million pixels is required.

Also, four digital pictures of the investigational product on the wound should be taken during the study (two photographs will be taken after investigational product application before the secondary dressing application on V1 and V2, and two pictures of the wound with the investigational product in place will be taken before the investigational product removal at both visits V2 and V3 (or Early termination visit, if performed instead of V3).

Table 2. Photographs schedule

Version 2.0 – March 29, 2019

	Inclusion visit (V1)	Intermediate visit (V2)	Additional visits	Final visit, or earlier if epithelization (V3)	Early termination visit (whenever possible)
Picture of the wound with the investigational product in place before the investigational product removal (but after removing the secondary dressing)		х		x	x
Picture of the lesion (after cleaning)	x	х		х	x
Picture after investigational product application before the secondary dressing application	х	х			

The pictures should be saved on a USB Key and sent to Lohmann & Rauscher for assessment. Two shipments of the study pictures are planned:

- first shipment should be performed shortly after the V1 of the first patient at each site; this data will additionally serve for the quality assessment of the photos, performed by the particular site. If necessary, additional training for the nurse will be organised. (NB! No quality confirmation is to be awaited from L & R team; further pictures may be taken as soon as planned, study nurse will be contacted only in case of quality issues).
- all remaining pictures for the first site patient and all other patients should be sent after LPLV at the site.

For processing the pictures will be loaded on a personal computer, and evaluated by W.H.A.T. (Wild et al., 2008).

The pictures should be performed only on the study wound and there should be no possibility to identify the patient. While saving the pictures on the PC and USB Key, the investigator should make sure that the files' names do not contain any sensible information like patient's name or other personal data. Only patient's number, study timeline and date of the photo could be used for the authentication.

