7.8.2.2 Secondary Objectives

Variables

Secondary efficacy criteria will be as follows:

- Complete healing at V3 (D21+2 or earlier, as soon as the wound is epithelialized completely).
- Wound condition assessment at V2 and V3 or ET
- Surrounding skin condition assessment at V2 and V3 or ET
- Global assessment of the dressing by the investigator at V2 and V3 or ET
- Global assessment of exudate management (efficiency of the CL to drain exudates to the secondary dressing)
- Global assessment of the dressing by the subject at V3 or ET
- Assessments from study nurse's booklet (at each dressing change)
- Adverse events (AEs), serious adverse events (SAEs), device effects (ADEs), serious device effects (SDEs), device deficiencies (DDs), occurring during the investigation

Measurements

Complete healing at V3

The evaluation of complete healing status (100% of epithelialization (first epithelia layer) of the wound) will be performed by the investigator at V3 (D21 \pm 2 or earlier if the wound is

healed before D21), as the phenomenon of epithelialization is visible to the naked eye). Data on complete healing will be reported in the CRF.

In addition to the evaluation of complete healing status performed by the investigator at V3, a blind assessment of healing will be performed by an independent assessor - chosen prior to the start of investigation - on photographs taken by investigators at V1 and at the final visit (V3). All photographs will be taken of the wound site and adjacent intact skin under standardized conditions (see Appendix 17.2). The digital photographs will be captured and available to the independent assessor chosen. A blind assessment of these photographs will be performed using W.H.A.T. in order to evaluate the healing status.

Wound condition assessment

Bleeding of the wound bed

The investigator will have to report the possible occurrence and intensity of bleeding at each dressing removal (including V1).

Maceration of the wound

Maceration refers to the skin changes seen when moisture is trapped against the skin for a prolonged period. The investigator will evaluate this parameter at each dressing removal (including V1).

Inflammation

The investigator will evaluate the presence of inflammation at the V1 and at each dressing removal.

• Infection

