7.9.1.2 Efficacy analyses

Analysis of the main criterion

The test for the non-inferiority of Lomatuell Pro® vs UrgoTul® for the main criterion will be carried out through a confidence interval (CI) approach. Non-inferiority will be established if the lower unilateral limit of the 97.5% CI in the PP population for the between-treatment difference (Lomatuell Pro® - UrgoTul®) in the percentage of wound dressing associated with a pain < 30 mm on VAS at V2 does not exceed -10%.

Considering that the studied population is "patients with an acute wound" and that the primary endpoint will be assessed at V2 (Day 3±2); we can expect very few drop-outs. We also expect few patients with a major protocol deviation. Therefore, we can conclude that an assumption of 10% attrition rate is acceptable for this study.

In order to unambiguously conclude to non-inferiority in agreement with most of guidelines, the same analysis will be performed on the mITT population. In case of missing data to evaluate the primary criterion, the subjects will be considered as failures. The trial will be considered positive if both approaches support noninferiority.

Adjustment

The frequency of analgesic intake will also be analysed. In case of a significant difference between the 2 dressing groups, the analysis of the primary criterion (painless dressing removals) will be adjusted using a Mantel-Haenszel test.

Analysis of the secondary criteria

The following statistical tests will be used to analyse the secondary criteria according to the criteria type:

- Qualitative nominal criteria will be compared using a Chi² test.
- Qualitative ordinal criteria will be compared using a Mann-Whitney-Wilcoxon test
- Quantitative criteria will be compared using an analysis of variance (ANOVA)

Degree of significance

The criteria for which the degree of significance of the bilateral test will not exceed 0.05 (statistically significant difference) will highlight the specificities between the 2 groups of dressing.

Percentage of complete healing at V3

A wound will be considered as completely healed when there is 100% of epithelialization (first epithelia layer) of the wound. The percentage of wounds healed will be calculated based on a blind assessment from photographs using W.H.A.T.

Assessment of the wound condition

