8 DATA MANAGEMENT

The sponsor provides all necessary technical equipment and documentation to the participating site or investigator, respectively. This includes study Clinical Investigation Plan, study nurses confirmation forms, CRFs, and contact details of the sponsor and monitor.

Data recording is conducted on paper-CRFs, except randomisation which is performed on IWRS.

All completed original CRF forms (as well as the study nurses diary) should be signed by the investigator and forwarded to RCTs within four weeks after completion at the latest. Additionally, pictures of wound will be provided to RCTs on an USB Key.

The data collected on the CRFs will be the data entered by RCTs and used for statistical analysis. Pictures of wound will be provided to RCTs on an USB Key for measurement by W.H.A.T, by Lohmann & Rauscher.

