10 QUALITY ASSURANCE

10.1 Quality assurance

All information about study subjects will be kept confidential. The CRFs will be pseudonymized. The CRFs will not contain any patient details like name, date of birth (only MM/YYYY will be collected), etc.

The CRF is the clinical data collection instrument for this study. All data requested on the CRF must be recorded. Missing data should be explained or filled in retrospectively by the respective investigator.

After data entry in the clinical data base (CDB), each data will be automatically checked and informatics queries may be issued.

These queries will be sent to the site in order to have them resolved in due time. The study nurses will have the help of RCTs within phone calls if necessary.

If any recording error has occurred on the CRF, straight line should be drawn through the incorrect entry and the correct data entered besides. The corrected information must be confirmed through initials and date by the investigator. Errors should not be blurred or erased.

The images gained during the course of the study will be evaluated by a blinded observer to reduce bias.

During the study, the study nurse coordinator will have regular contacts with the investigation site. It is planned to have also audit visits. Data in the CRF will be considered as source document, except for demographics and inclusion/exclusion criteria and randomisation reports. Moreover, the study nurse will have their own nursing record in which the main information regarding the care will be noted (i.e.: name, patient coordinates, date of care, act of care and comment).

It has to be verified the clinical study is conducted according the CIP, and subsequent amendments, and the applicable legal requirements.

All documents associated with the present study are archived for a period of 15 years at the sponsor's site, study nurse site and at study nurse coordinator's site.

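### The photographic healing reading is called blind and independent, but the protocol gives it to the sponsor and has no step that keeps dressing pictures from the reader

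*Protocol*

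**What the plan says.** On who reads, and how:

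- Protocol 7.8.2.2 says that, besides the investigator's own judgement of healing, "a blind assessment of healing will be performed by an independent assessor - chosen prior to the start of investigation". That reading uses the V1 and V3 photographs.
- Protocol 7.9.1.2 bases the endpoint on it: "The percentage of wounds healed will be calculated based on a blind assessment from photographs using W.H.A.T".
- Protocol 10.1 adds a general commitment: "The images gained during the course of the study will be evaluated by a blinded observer to reduce bias".
- Protocol 7.7 says: "The evaluation by the W.H.A.T. system will be performed by Lohmann & Rauscher with the photographs sent by RCTs on USB Keys". Section 8 agrees: "Pictures of wound will be provided to RCTs on an USB Key for measurement by W.H.A.T, by Lohmann & Rauscher".

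On what is photographed, labelled and sent:

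- Section 7.7 asks for one lesion picture at each of the three visits. In addition, "four digital pictures of the investigational product on the wound should be taken during the study".
- After the schedule that lists both types (Table 2), section 7.7 sends the pictures to the sponsor in two shipments. The first follows V1 of each site's first patient and also serves as a photo quality check. The second contains everything that remains. Neither is split by picture type.
- On file names: "Only patient's number, study timeline and date of the photo could be used for the authentication".
- Appendix 18.1 requires the patient's ID and the date to be legible on the ruler in the lesion picture. Under section 15 that ID is made up of the site number and the patient's number within the site.

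**The concern.** The trial is open-label. The investigator's judgement of healing, the wound and skin scores and the product ratings all come from people who know which dressing was used. The photographic reading is the one healing measure that the plan describes as shielded from that knowledge, and the percentage of healed wounds is calculated from it.

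Two features weaken that shield. First, the reading is done in an organisation with an interest in the result, while another section calls the assessor independent. Second, the same organisation receives pictures of the dressing on the wound under the patient number that also identifies the lesion pictures. If the study report describes the healing result as blinded and independently assessed, the protocol would not by itself support that description.

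**Working it through.** The point is about procedure, so the check traces the reader, the pictures and the identifiers through the protocol.

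**1. Plan's own figure, for context.** Section 7.9.2 gives 75 per group, then 84. Using n = (1.960 + 0.842)² × 2 × 0.95 × 0.05 / 0.10² = 7.849 × 9.5 = 74.6, n rounds up to 75. With 10% attrition, 75 / 0.90 = 83.3, so 84. Both figures reproduce. They concern the primary VAS endpoint, and the present point changes neither.

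**2. Who reads.** Sections 7.7 and 8 name the sponsor. Section 7.8.2.2 says an independent assessor, and section 10.1 a blinded observer. No section says how a reader inside the sponsor would be independent, or of whom.

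**3. What reaches the reading organisation.**

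| Picture type | Per patient | × 168 patients |
|---|---|---|
| Lesion, cleaned (V1, V2, V3 or early termination) | 3 | 504 |
| Dressing in place (V1 once, V2 twice, V3 or early termination once) | 4 | 672 |
| Total | 7 | 1,176 |

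These are maxima. A wound already healed at V2, or an early termination, lowers them. The V1 schedule includes a dressing-in-place picture, so such a picture is planned even for patients who heal before V2.

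**4. Whether the two types can be linked.** The permitted file-name elements (patient number, study time point, date) are the same for both. Renaming files alone would not break the link, because the ID is also inside the lesion image on the ruler.

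**5. Whether any step breaks the link.** Sections 7.7, 7.8.2.2, 8 and 10.1 and Appendix 18.1 describe no recoding, no filtering by picture type, no masking and no barrier between the reader and the dressing pictures. Section 7.9.3 controls access to the randomisation list, but that does not cover what the pictures themselves show. The SAP supplied is written for the protocol of another product (Suprasorb C) and adds no image-blinding procedure for this trial.

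**6. What the healing reading needs.** Section 7.8.2.2 bases it on V1 and V3 photographs of the wound and adjacent skin. Section 7.7 has the dressing removed and the wound cleaned first. The dressing-in-place pictures are therefore not needed for it. The reading itself needs 2 × 168 = 336 lesion pictures, or 504 if V2 is also measured.

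**The case against.** The strongest reply is that blinding is promised in three places, so what is missing is operating detail that a study manual could supply. As to the commitment, this stands. But the protocol does more than leave a gap: it assigns the reading to the sponsor and sends it both picture types under one number. Carried out exactly as written, that works against the promise.

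A second reply is that the dressing pictures are not described as input to the healing reading, that section 8 speaks only of wound pictures, and that RCTs handles the keys and could filter them. All of this is fair. It shows that the remedy is easy, but no filtering step is written.

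A third is that an independent assessor could be a person whom the sponsor appoints and who is independent of the investigators. That reading is possible. The wording is then ambiguous and needs to be settled.

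A fourth is that full epithelialisation is said to be visible to the naked eye and is also recorded by the investigator. This limits the room for subjective reading. The investigator's record is open-label, though, so it cannot replace a blinded reading.

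A reader might go further and infer that the assessor will see the allocation, or that the healing endpoint has no blinding at all. The documents do not support either. The first needs two facts that they do not give: that the person reading opens the dressing pictures, and that the two dressings can be told apart in a photograph. Section 5 calls the products rather similar. Sections 7.4.1 and 7.4.2 describe a wide-meshed tulle and a polyester mesh, which suggests a visible difference but does not establish one. The second ignores the commitments in 7.8.2.2, 7.9.1.2 and 10.1.

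**Conclusion.** The point holds in this form: the protocol states that the photographic healing reading is blind, but does not secure it, and its sections disagree on whether the assessor is independent. Nothing written prevents the reader from linking a lesion picture to a picture of the dressing on the same patient.

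The scope is the W.H.A.T.-based secondary endpoint of complete healing at V3. The primary VAS endpoint, its non-inferiority test and the sample size are not affected.

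The size of any bias cannot be quantified. A figure would need a healing rate and a rate of altered readings, and the documents give neither. The conclusion rests on the text of the protocol and assumes only that no separate, unpublished procedure fills the gap. The matter should be corrected, but it does not threaten the trial's main conclusion.

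**What to change.** 1. State that all keys go to RCTs first, and that RCTs passes to the healing reader only the cleaned-lesion pictures.
2. Replace file names with random codes. Mask the patient ID on the ruler while keeping the scale, or put a random code on the ruler instead.
3. Withhold dressing-in-place pictures from the reader until the healing readings are locked.
4. Have the first-shipment quality check done by RCTs, or by sponsor staff who do not read the healing pictures.
5. Make sections 7.7, 7.8.2.2, 8 and 10.1 name the same assessor, without access to the randomisation list. If that assessor is sponsor staff, drop the word independent.

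The cost is corrected wording, some file handling at RCTs and the masking of up to about 504 lesion pictures. A random code on the ruler would avoid most of the masking for pictures not yet taken. No extra reader, patient or visit is needed.
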